6.2. Description of Evaluations

6.2.1 Screening Evaluation

Consenting Procedure

We are requesting a waiver of informed consent and a waiver of HIPAA authorization (see section 4.3).

Screening

This is not applicable, because the study will include all community-dwelling Medicare beneficiaries with dementia who have been attributed to NYQC and had

fragmented care in the past 12 months. All of these criteria will be measured using claims, not interactions with patients or proxies.

6.2.2 Enrollment, Baseline, and/or Randomization

Enrollment

The enrollment date for all participants will be the date of randomization.

Baseline Assessments

The research assistant will manually review the EHR for participants' demographic characteristics (age, race, sex, co-morbidities).

Randomization

See section 6.1 for a timeline of randomization, intervention, and follow-up.

6.2.3 Follow-up Visits

Follow-up visits per se are not applicable to this trial. The length and frequency of interactions between the care coordinator and patient or proxy will vary with the patient's needs and care coordinator's discretion.

6.2.4 Completion/Final Evaluation

A completion or final evaluation visit is not applicable to this trial. The length and frequency of interactions between the care coordinator and patient or proxy will vary with the patient's needs and care coordinator's discretion. The ED and hospitalization outcomes will be measured in claims.

7 SAFETY ASSESSMENTS

7.1 Specification of Safety Parameters

This is not a drug trial, so we will not be assessing safety with laboratory values. See below for how we will monitor safety in this trial.

7.2 Methods and Timing for Assessing, Recording, and Analyzing Safety Parameters

This is not a drug trial, so we will not be assessing safety with laboratory values. See below for how we will monitor safety in this trial.

7.3 Adverse Events and Serious Adverse Events

Adverse Event (AE): Any untoward or unfavorable medical occurrence in a clinical research study participant, temporally associated with the participants' involvement in the research, whether or not considered related to participation in the research.

AEs for this study: AEs may include a mild increase in anxiety or stress on the part of the patient or patient's healthcare proxy. This may be expected from a discussion about the challenges of navigating healthcare, but is expected to be short-lived, due to the provision of resources to address the problem.

Serious Adverse Event (SAE): Any adverse event that:

- Results in death

- Is life threatening, or places the participant at immediate risk of death from the event as it occurred
- Causes persistent or significant disability or incapacity
- Is another condition which investigators judge to represent significant hazards

SAEs for this study: Because the study population consists of PLWD, the possibility of emergency department visits and hospitalizations may be reasonably expected. The occurrence of these events will be measured by the study as outcomes, and it is hypothesized that the intervention group will have fewer of these events than the control group. Because the study population consists of PLWD, the possibility of death is also an expected occurrence, though it is not expected to be related to the intervention. We will monitor for this event as well, although it is not a study outcome per se.

7.3.1 Reporting Procedures

Process for identifying AEs and SAEs:

If the care coordinators perceive that a patient or healthcare proxy has increased anxiety, the care coordinator will report this to the PI, who will consult with the research team's geriatrician. The geriatrician can discuss the case with the care coordinator and also with the patient's physicians.

The research team will analyze Medicare claims monthly to monitor for the outcomes of emergency department visits and hospitalizations. These are expected events that will be tracked and reported to the PI.

Any deaths that are detected through review of electronic health records by the care coordinators or research assistant will be reported to the PI.

Any unanticipated problems encountered by team members will be reported to the PI.

Severity of Event

All AEs will be assessed for severity by the PI using the following scale:

- Mild – Events require minimal or no treatment and do not interfere with the participant's daily activities.
- Moderate – Events result in a low level of inconvenience or concern with the therapeutic measures. Moderate events may cause some interference with functioning.
- Severe – Events interrupt a participant's usual daily activity and may require systemic drug therapy or other treatment. Severe events are usually potentially life-threatening or incapacitating. Of note, the term "severe" does not necessarily equate to "serious."

Relationship To Study Intervention

All adverse events (AEs) will have their relationship to study intervention assessed by the PI who will evaluate the situation based on temporal relationship and his/her clinical judgment. The degree of certainty about causality will be graded using the categories below. In a clinical trial, the study product must always be suspect.

- Definitely Related – There is clear evidence to suggest a causal relationship, and other possible contributing factors can be ruled out. The clinical event occurs in a plausible time relationship to study intervention administration and cannot be explained by other factors.
- Possibly Related – There is some evidence to suggest a causal relationship. However, other factors may have contributed to the event (e.g., the participant’s clinical condition, other concomitant events). Although an AE may rate only as “possibly related” soon after discovery, it can be flagged as requiring more information and later be upgraded to “probably related” or “definitely related,” as appropriate.
- Not Related – The AE is completely independent of study intervention administration, and/or evidence exists that the event is definitely related to another etiology. There must be an alternative, definitive etiology documented by a qualified medical professional.

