Care coordinators will administer this survey by telephone to participants (patients or proxies) in the intervention group. The care coordinators will document the survey responses in customized data entry form in REDCap, a secure web-based data management platform.³⁶ If the patient or proxy responds to the survey in a way that indicates a perceived problem with care coordination in the past 6 months (i.e., a "positive" response to ≥ 1 of 8 questions, as defined previously),³⁴ then we will consider this a "positive screening." Care coordinators will be trained in advance to recognize "positive" responses and respond to them in real time, asking open ended questions to understand why the respondent felt that there was a problem with care coordination. For patients and proxies whose screening calls were "negative" (not revealing a perceived problem with care coordination), the care coordinators will give them their contact information and invite them to reach out with any questions or concerns. NYQC considers administration of this survey to be part of clinical care.

We will have a data analyst review the survey responses to measure (as part of the implementation measure for fidelity) whether surveys were correctly categorized as positive or negative.

For the control group, an administrator at NYQC is responsible for querying daily the

Epic EHR to identify discharges from NYQC hospitals and for querying daily a New York City health information exchange called NYCLIX to identify hospital discharges from non-NYQC hospitals.^{37,38} (An emergency department visit that results in discharge to home without hospital admission does not qualify.) The administrator assigns each discharged patient to a care coordinator, who then reaches out to the patient by phone.

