Additional considerations: The research team carefully considered how to handle several complexities that are interrelated. (1) Consistent with standard practice in which patients are followed for a maximum of 1 year, patients in the usual care group may continue to have events that qualify them for care coordination beyond the 3-month timeframe that we have specified for the “qualifying event window.” That is, patients in the usual care group will continue to be assigned care coordinators when they are hospitalized and discharged. (2) Patients randomized to the intervention group may be hospitalized during the first 3-month qualifying-event-window and after that window as well. (3) Patients randomized to the intervention group may be referred by their physicians for care coordination, just as that occurs for about 5% of the usual care participants. To address these complexities, we have developed the following approach. If a physician refers a

patient who is assigned to the intervention group to care coordination, we will honor that referral and provide care coordination. If a patient in the intervention group has a hospital admission at any time (during the first 3-month qualifying window or during follow-up), we will administer the perceptions of care coordination survey after discharge and provide care coordination if the survey indicates a need. We believe this is more ethical than not providing care coordination at all to discharged patients in the intervention group; assignment of care coordinators would still be made based on reported problems with care coordination and not given automatically. Thus, during the 3-month window for qualifying events, all participants in the intervention group will receive the survey; after that, the survey will be given to those intervention participants who are discharged from the hospital.

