5.4 Adherence Assessment

[figure not shown]
We will measure different versions of adherence when we collect implementation outcomes for the secondary objective of the study. These implementation outcomes will be collected by a research assistant, who will review the EHRs for participants in both study groups. The research assistant will extract data from the EHRs manually, using a structured form in REDCap. The following implementation outcomes will be collected: acceptability (percent of participants who engage with the care coordinators in both groups), appropriateness (types and frequencies of different care coordination services provided in both groups), fidelity (percent of eligible individuals who receive care coordination services based on perceived need in the intervention group), and efficiency (total number of care coordinator hours in both groups). These implementation outcomes are drawn from the Consolidated Framework of Implementation Research (CFIR) and related work by Proctor et al.³⁹⁻⁴¹

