7.3.2 Follow-up for Adverse Events

The occurrence of an adverse event (AE) or serious adverse event (SAE) may come to the attention of study personnel during interactions between care coordinators and study participants and their proxies. The occurrence of an AE or SAE may also come to the attention of study personnel upon review of medical records.

All AEs will be captured on the appropriate case report form (CRF). Information to be collected includes event description, time of onset, qualified medical professional’s assessment of severity, relationship to study, and time of resolution/stabilization of the event. All AEs occurring while on study must be documented appropriately regardless of relationship. All AEs will be followed to adequate resolution.

Changes in the severity of an AE will be documented to allow an assessment of the duration of the event at each level of severity to be performed.

Reporting schedule:

- All **adverse events that are serious (SAE) and unexpected** (i.e., have not been previously reported for the study’s intervention) will be reported to the IMPACT Collaboratory Regulatory and Data Team and NIA IMPACT Collaboratory PO for dissemination to the IMPACT Collaboratory DSMB Chair (or the project’s Safety Officer) within 48 hours of the study’s knowledge of SAE.
 - Only those adverse events that are serious (SAE), unexpected, **and related to the intervention** must also be reported to Advarra IRB. Unexpected and **unrelated** SAEs will be reported to Advarra IRB on a case-by-case basis if requested by the IMPACT Collaboratory DSMB Chair (or the project’s Safety Officer) or NIA IMPACT Collaboratory PO.
- All unexpected deaths will be reported to IMPACT Collaboratory Regulatory and Data Team and NIA IMPACT Collaboratory PO for dissemination to the IMPACT Collaboratory DSMB Chair (or the project’s Safety Officer) within 24 hours of study’s knowledge of death.

- Advarra IRB does not require the specific reporting of death outside of the SAE reporting requirement above, but they will be notified on a case-by-case basis if requested by the IMPACT Collaboratory Chair (or the project's Safety Officer) or NIA IMPACT Collaboratory PO.

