9 STATISTICAL CONSIDERATIONS

9.1 General Design Issues

The trial is based on the hypothesis that assigning care coordinators to PLWD whose care partners' perceive a problem with care coordination will result in fewer ED visits and hospitalizations than assigning care coordinators to PLWD at the time of hospital

discharge. To avoid circularity, we will separate exposures and outcomes in time. That is, we will have a 3-month exposure period, during which a hospitalization that prompts care coordination will only be counted for the exposure and not as an outcome.

The 3-month time period was chosen, based on preliminary data suggesting that more fragmented care over 12 months independently increases the risk of an incident ED visit^(under review) or incident hospital admission²¹ in the subsequent 1-3 months, compared to less fragmented care.

A parallel design was chosen because it is a robust design that allows for concurrent comparisons. The outcome of ED visit or hospitalization will be measured using Medicare claims data, which are the gold standard, because they capture events across health systems and are thus broader than EHRs.

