9.2 Sample Size and Randomization

The primary outcome is the number of events (emergency department visits or hospitalizations) / person-time alive. Preliminary data (for the control group) show an average event rate per person of 1.99 events over 334 live days (0.92 years). Using Poisson regression, with a sample size of 688 PLWD and assuming 20% attrition and $\alpha = 0.05$, we have >90% power to find an event rate ratio of 0.74 (i.e., a reduced event rate of 1.47 or lower in the intervention group vs. 1.99 in the control group), which is a meaningful difference. Data will be analyzed using an intention-to-treat approach. We will use descriptive statistics to report our secondary implementation outcomes; these are designed to inform future iterations and dissemination of this intervention, rather than test hypotheses per se.

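### Deaths are found by EHR review and coordinator contact, which may differ by arm; add both-arm death dates to the monthly Medicare run and use them to end person-time alive

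*Combined protocol and SAP*

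**What the plan says.** **Finding deaths.** Section 7.3.1 reads: "Any deaths that are detected through review of electronic health records by the care coordinators or research assistant will be reported to the PI". Section 7.3.2 says that AEs and SAEs "may come to the attention of study personnel during interactions between care coordinators and study participants and their proxies", or on review of medical records. Section 7.3 counts death among SAEs.

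**Claims.** Section 7.3.1 also reads: "The research team will analyze Medicare claims monthly to monitor for the outcomes of emergency department visits and hospitalizations". Death is not listed. Section 9.1 prefers claims for the outcome "because they capture events across health systems and are thus broader than EHRs".

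**Who is contacted.** Under section 5.2, "during the 3-month window for qualifying events, all participants in the intervention group will receive the survey". For usual care, the same section describes daily searches for hospital discharges: "The administrator assigns each discharged patient to a care coordinator, who then reaches out to the patient by phone". Physician referral is open to both arms. On the research assistant, section 5.4 says: "These implementation outcomes will be collected by a research assistant, who will review the EHRs for participants in both study groups".

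**What deaths are used for.** Sections 8 and 9.3 plan no interim analysis. They name one finding that might prompt a safety review, the number of unexpected deaths, which a statistician examines by group. In sections 9.2 and 9.5 the primary outcome is events divided by person-time alive. Section 9.2 reports: "Preliminary data (for the control group) show an average event rate per person of 1.99 events over 334 live days (0.92 years". Section 6.1 lists three data sources (survey, EHR, claims) and assigns date of death to none of them.

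**The concern.** A comparison of deaths by group is informative only if deaths are looked for equally hard in both groups. Here one set of observers, the coordinators, meets the arms on different terms by design. They are to call every intervention participant during the qualifying window, but they reach a usual-care participant only after a discharge or referral. A usual-care participant who dies at home or in another health system without such a contact could go unnoticed by this route. The reporting clock in 7.3.2 starts when the study learns of the death, so detection determines what the DSMB sees.

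The protocol already has a both-arm data stream and argues that claims see more than EHRs, but it does not use that stream for deaths.

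The secondary issue is the primary denominator. A missed death leaves event-free time in person-time alive and lowers that arm's rate. Because no source for the death date is named, a reader cannot confirm that the denominator is built identically in both arms.

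**Working it through.** **1. Ascertainment by arm and period**

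- *Coordinators, first 3 months.* Intervention: everyone is to be surveyed. Usual care: contact after discharge or referral. This is clearly unequal (sections 3 and 5.2).
- *Coordinators, after the window.* Intervention: survey after a hospital discharge. Usual care: contact after a discharge. These are broadly similar. Screen-positive participants may still be receiving coordination, for up to 1 year (section 3), but so may usual-care participants who qualified.
- *Research assistant.* Reviews EHRs in both arms, for baseline characteristics (6.2.2) and implementation outcomes (5.4, 9.4.2). No review date and no end-of-follow-up vital-status check are given.
- *Monthly claims.* Not restricted by arm, but stated only for ED visits and hospitalizations.

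Unequal finding of deaths is therefore a real possibility, concentrated in the qualifying window. No detection rate is given for either arm.

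**2. The plan's own power figure**

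Inputs from 9.2: 688 participants, 20% attrition, alpha 0.05, means 1.99 and 1.47, stated power above 90%.

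- n per arm = 344 × 0.8 ≈ 275
- SE of the log rate ratio = √[1/(275 × 1.99) + 1/(275 × 1.47)] = 0.0656
- |ln(1.47/1.99)| / 0.0656 = 4.62; power = Φ(4.62 − 1.96) = 99.6% two-sided

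This agrees with the stated lower bound. Power falls to 90% at a variance-to-mean ratio of about 2.0.

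**3. Illustration: EHR-detected deaths used to end person-time**

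Assumptions: the whole shortfall of 365 − 334 = 31 days is due to death; true live time is the same in both arms; usual care misses an excess share m of the 31 days and the intervention arm misses none.

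Observed RR = true RR × (334 + 31m)/334

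- m = 0.25: 341.75/334 = 1.023; a true 0.74 reads 0.757
- m = 0.50: 349.5/334 = 1.046; a true 0.74 reads 0.774
- m = 1.00: 365/334 = 1.093; a true 0.74 reads 0.809

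If both arms miss some time, the factor is (334 + 31 × miss in usual care)/(334 + 31 × miss in intervention). With 50% and 20%, 349.5/340.2 = 1.027; with 30% and 10%, 343.3/337.1 = 1.018.

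Consequences at 275 per arm, for m = 0.25, 0.50 and 1.00:

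- Power at a true RR of 0.74, pure Poisson: 99.6% becomes 98.9%, 97.4% and 89.9%.
- The same with a variance-to-mean ratio of 2: 90.1% becomes 85.1%, 78.7% and 62.9%.
- Two-sided rejection at a true RR of 1, pure Poisson: 5% becomes 6.7%, 11.7% and 31.2%, with the shift against the intervention.

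If the intervention arm missed more deaths, the sign would reverse; 0.74 would read 0.723, 0.707 and 0.677.

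The 9.3% ceiling covers deaths within the 12-month follow-up only. A participant without a qualifying event starts follow-up at month 4 (section 6.1). If such a participant died before then unnoticed, a full event-free year would be added. The documents give no figure from which to size this.

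**The case against.** A reader might infer more than the documents support: that EHR review is the only way deaths are found, that deaths will be found unequally, and that the primary rate ratio is therefore biased. There are good answers to each step.

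- *Only route.* Section 7.3.2 adds coordinator contact with participants and proxies. This corrects the inference, but that route also depends on arm, so it does not remove the concern.
- *Unequal as a fact.* The research assistant reviews EHRs in both arms and could even out detection if the review runs to the end of follow-up. Nothing says that it does, so inequality remains a risk, neither established nor excluded.
- *Timing.* The universal intervention call falls mostly before primary follow-up, and one survey call cannot detect a later death. This stands. It weakens any firm claim about direction or size during follow-up.
- *Primary analysis.* Section 7.3.1 is a safety procedure. Nothing says that EHR-detected deaths end person-time; claims are the stated source for the primary outcome events, and the preliminary 334 live days imply that some vital-status source already exists. This stands. What remains is an unnamed source, not a demonstrated bias.
- *Safety consequence.* Section 7.3 treats death as expected in this population and not as a study outcome, and the trigger concerns unexpected deaths. That narrows the consequence. However, a death must be detected before anyone can judge whether it was unexpected, and the review is by group.

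**Conclusion.** The point holds in a limited form. The stated procedure for finding deaths relies partly on coordinator contact that is more intensive in the intervention arm, at least in the qualifying window, and it leaves out the both-arm claims run. This could distort the by-group review of unexpected deaths, the only safety trigger named. The documents do not allow the size of that distortion to be estimated.

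For the primary analysis, the finding is a missing specification. If the death date already comes from Medicare data, the person-time bias disappears and only the safety gap remains. If EHR-detected deaths were used, the rate ratio would be inflated by about 2.3% to 4.6% for a 25% to 50% excess of missed time in usual care, with a ceiling of 9.3% for deaths within follow-up. These figures rest on assumed miss rates, an assumed direction, and all 31 lost days being due to death. An error of this kind would be modest, but a larger sample would not remove it.

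**What to change.** **Section 7.3.1:** add vital status and date of death, for all participants in both arms, to the monthly Medicare data run. Keep EHR and coordinator reports for prompt notification, because Medicare death dates may lag and 7.3.2 sets a 24-hour limit from knowledge of an unexpected death.

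**Section 9.5:** name the source of the death date, and state that this one arm-neutral date ends person-time alive in both arms. If it is the source behind the preliminary 334 live days, say so.

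**Cost:** a few lines of text and an additional item in an existing monthly run. The documents do not confirm that the ACO's Medicare files carry a death date, so the sponsor should check this first. If they do not, the plan should name another source that is checked on the same schedule in both arms. Sample size, intervention and outcome definition are unchanged.
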